- State- Trait Anxiety Inventory (STAI)
- Average weekly frequency of migraine headaches for the last 4 week period
- COMPASS-31 score.

Anthropomorphic assessments (body weight, body height, body mass index [BMI]. Pregnancy test results that need to be recorded from chart review or obtained as part of the screening and EKG to rule out any abnormal baseline electrocardiogram such as second and third degree heart block, atrial fibrillation, atrial flutter, recent history of ventricular tachycardia or ventricular fibrillation, or clinically significant premature ventricular contraction, history of prolonged QT interval or a history of clinically significant arrhythmia.

Data will be captured on REDCAP and stored on the secure Hopkins server for this purpose.

2. Treatment Start Visit

At this visit, the patient will receive the gammaCore (nVNS) device and a video instruction will be use to explain how to properly handle the device. Treatment can only start after eligibility has been fully checked and all data collected at screening have been keyed into the trial database. Women of childbearing potential must have a negative urine pregnancy test.

After eligibility is confirmed with the clinical center staff the treatment can begin. The date of starting treatment is the start (ZERO) time for the timing of follow-up visits.

Frequency and duration of nVNS treatment.

The treatment will be self-administered using nVNS and will be applied for 8 weeks; 4 weeks will be used on one side of the neck and other 4 weeks in the contralateral side. A member of the study will provide the proper training on the correct use of nVNS. The patient will be instructed to use the nVNS in place of the rescue medications. When the nauseas gets bad enough that they feel to use a rescue medication they will first use the device on one side of the neck for two 2minute stimulations and wait fifteen minutes to check if the stimulation works. If this does not help either, they will stimulate with an additional 2 stimulations and wait for another fifteen minutes. If there is no improvement rescue medication will be used. nVNS can be used up to, but no more than, 8 times a day.

3. Follow-up Visits

Patients will return for follow-up visits at 4 and 10 weeks after treatment initiation. The specific

procedures to be completed at each of the follow-up visits are:

- Week 4 visit: The following questionnaires should be completed and collected:

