 - Gastroparesis Cardinal Symptom Index Daily Diary (GCSI-DD)
 - Rescue medication uses daily diary- number of pills and type
 - Migraine and headache daily diary
 - Gastrointestinal Symptom Rating Scale (GSRS)
 - Patient Assessment of Upper Gastrointestinal Symptom Severity Index (PAGI-SYM)
 - Beck Depression Inventory (BDI-II)
 - State- Trait Anxiety Inventory (STAI)
 - Average weekly frequency of migraine for the last 4 week period
 - COMPASS-31 score.
 - Global patient impression (GCPI) questionnaire.

Laboratory test results that need to be collected are EKG and urine pregnancy test. Review study of adverse events will be addressed.

- Week 8 visit: This will be the end of study visit. A medical history, including side effect or symptom profile will be collected. The following questionnaires should be completed and collected:
 - Gastroparesis Cardinal Symptom Index Daily Diary (GCSI-DD)
 - Rescue medication uses daily diary- number of pills and type
 - Migraine and headache daily diary
 - Gastrointestinal Symptom Rating Scale (GSRS)
 - Patient Assessment of Upper Gastrointestinal Symptom Severity Index (PAGI-SYM)
 - Beck Depression Inventory (BDI-II)
 - State- Trait Anxiety Inventory (STAI)
 - COMPASS-31 score.
 - Global patient impression (GCPI) questionnaire.
- Week 10 visit: This will be the end of study visit. A medical history, including side effect or symptom profile will be collected. The following questionnaires should be completed and collected:
 - Gastroparesis Cardinal Symptom Index Daily Diary (GCSI-DD)
 - Rescue medication uses daily diary- number of pills and type
 - Migraine and headache daily diary
 - Gastrointestinal Symptom Rating Scale (GSRS)
 - Patient Assessment of Upper Gastrointestinal Symptom Severity Index (PAGI-SYM)
 - Beck Depression Inventory (BDI-II)
 - State- Trait Anxiety Inventory (STAI)
 - COMPASS-31 score.
 - Global patient impression (GCPI) questionnaire.

	Screening & GammaCore treatment Visits (Weeks)		Follow-up Visits: Weeks from start of treatment		
	Screening (0)	Treatment initiation (2)	4	8	10
Consent	X				
Baseline medical	X				
history					
GCSI-DD	X		X	X	X
Rescue Medication Daily Diary	X		X	X	X
Migraine and Headache Daily Diary	X		X	X	X
Collection of GCSI- DD		X	X	X	X
Collection of Rescue Medication Daily Diary		X	X	X	X
Collection of Migraine and Headache Daily Diary		X	X	X	X
PAGI-SYM questionnaire	X		X	X	X
GSRS questionnaire	X		X	X	X
Beck Depression Inventory-II	X		X X	X X	X X

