- Currently implanted with an electrical and/or neurostimulator device, including but not limited to cardiac pacemaker or defibrillator, vagal neurostimulator, deep brain stimulator, spinal stimulator, bone growth stimulator, or cochlear implant.
- History of carotid endarterectomy or vascular neck surgery on the right side.
- Implanted with metal cervical spine hardware or has a metallic implant near the gammaCore stimulation site.
- Any other condition, which in the opinion of the investigator would impede compliance or hinder the completion of the study.
- Failure to give informed consent.

6. **Drugs/ Substances/ Devices**

gammaCore Sapphire (nVNS) ²³⁻²⁵

Description:

nVNS is a multi-use, hand-held, rechargeable, portable device consisting of a rechargeable battery, signal-generating and -amplifying electronics, and a control button for the patient to control the signal amplitude. The device provides visible (display) and audible (beep) feedback on the device and stimulation status. A pair of stainless steel surfaces, which are the skin contact surfaces ("stimulation surfaces"), allow the delivery of a proprietary electrical signal. The patient applies electroCore-approved gel to the stimulation surfaces to maintain an uninterrupted conductive path from the stimulation surfaces to the skin on the neck. Tubes of electroCore-approved gel are provided with each unit and refill kit for this purpose. The stimulation surfaces are capped when not in use.

7. Study Statistics

Data analysis will be performed at Mayo Clinic Scottsdale, Arizona by [name], ([contact]). This site will no recruit participants.

Johns Hopkins will serve as coordinating center, responsible for overall data management, monitoring and communication among both sites, and general oversight of the conduct of this protocol.

Outcome measures

Primary: The primary outcome measure is the average daily use of rescue medications for exacerbation of nausea/vomiting.

Sample size justification

- Primary endpoint: Improvement in nausea control, as defined by a 50% reduction n the number of weekly doses of rescue medications, compared with baseline.

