- Total of 45 patients. This is a pilot study to assess the strength of the signal (improvement) with peripheral VNS for nausea. Since there is evidence that the left and right vagus may have different pathways within the CNS, with the left side being dominant in innervation of center involved in food aversion and nausea (Cell 175, 665–678, 2018), we are proposing to study three groups as follows
 - Group 1; Start with left sided stimulation 15 patients
 - Group 2. Start with right sided stimulation 15 patients
 - Group 3. Both sided stimulation 15 patients
- Our assumptions are as follows, in terms of the number of patients improving in each group

Group 1: 4/15 Group 2: 11/15 Group 3: 7/15

If these assumptions are true, the type I error will be < 0.05

8. Risks³²⁻³⁴

The adverse reactions observed in nVNS studies include:

- i. Shortness of breath (dyspnea), hoarseness, or change in voice during treatment.
- ii. Muscle twitching, discomfort, or pain during stimulation.
- iii. Change in taste (dysgeusia).

These first three reactions resolved after treatment was completed.

- iv. Local skin irritation/inflammation.
- v. Any progression of headache symptoms.

Adverse reactions not seen in the studies, but associated with implanted vagal nerve stimulation devices include:

- vi. Tingling, pricking, or a feeling of "pins and needles" on the skin where the device is applied (paresthesia or dysaesthesia) lasting beyond the treatment period.
- vii. Fainting (syncope), light-headedness, and/or dizziness.
- viii. Sweating.
- ix. Fatigue, depressed mood.
- x. Tinnitus.
- xi. Diarrhea.
- xii. Abnormal heart rhythm.

Adverse events will be evaluated in every follow-up visit. A form of Adverse Event will be completed if the candidate complains of any symptoms, sign, abnormal assessment or any combination of these. An adverse event can be expected side effect that is of a serious nature, or an unexpected side effect/event regardless of severity.

This study will monitor and report adverse events to ensure patient safety to IRB and FDA. Signs and symptoms associated with the adverse event will be graded as to severity by the clinical site staff as mild, moderate, or sever using Version 5.0 of the National Cancer Institute's Common Terminology Criteria for Adverse Events (CTCAE).

9. Benefits

Description of the probable benefits for the participant and for society.

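### Groups 1 and 2 each get both sides of the neck in opposite order, but the left/right question is framed as a between-group responder count with no on-treatment window and no crossover analysis

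*Combined protocol and SAP*

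**What the plan says.** Section 4 (Frequency and duration of nVNS treatment) gives eight weeks of self-administered treatment, of which "4 weeks will be used on one side of the neck and other 4 weeks in the contralateral side". It does not mention groups.

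Section 7 (Sample size justification) introduces three groups because the left and right vagus may act differently on nausea. Two of them are defined by where they begin: "Group 1; Start with left sided stimulation 15 patients" and "Group 2. Start with right sided stimulation 15 patients". Group 3, also 15 patients, is stimulated on both sides. The planning statement reads "Our assumptions are as follows, in terms of the number of patients improving in each group", followed by "Group 1: 4/15 Group 2: 11/15 Group 3: 7/15", and concludes that the type I error will then be below 0.05. No test is named and no power is given.

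The outcome is described twice in Section 7. Under Outcome measures: "The primary outcome measure is the average daily use of rescue medications for exacerbation of nausea/vomiting". Under Sample size justification: "Improvement in nausea control, as defined by a 50% reduction n the number of weekly doses of rescue medications, compared with baseline". Neither says which treatment weeks are compared with baseline. No washout, carry-over assumption, within-patient analysis or method of assigning patients to groups is stated.

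The visit table in Section 4 has a row "Collection of Rescue Medication Daily Diary" marked at treatment initiation and at weeks 4, 8 and 10, and the diary is filled in daily. Rescue use on each side can therefore be separated.

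**The concern.** By the end of week 8, a Group 1 patient and a Group 2 patient have both had four weeks on each side. They differ in order only. A between-group comparison therefore depends on the window:

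- **Weeks 1-4:** left against right, before any switch, so free of carry-over.
- **Weeks 5-8:** right against left, open to carry-over from the first side.
- **Weeks 1-8:** equal time on each side in both groups. With no carry-over, order or period effect, the expected difference is zero.

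All three fit the plan's wording. The three-group assumption is the only stated basis for 45 patients, so what is at stake is the comparison those numbers were meant to serve. A whole-treatment analysis, which the plan permits, could miss a real side difference. In an open-label study, choosing the window after seeing the data would leave the result open to selection.

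**Working it through.** **Inputs from Section 7.** 15 patients per group; assumed responders 4/15 = 26.7%, 11/15 = 73.3%, 7/15 = 46.7%.

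**Assumptions, not in the documents.** 4/15 and 11/15 are four-week rates for left (L) and right (R). A share c of the first side's effect persists into weeks 5-8, with c from 0 to 1. There is no period effect.

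**The plan's own figure.** Total responders are 4 + 11 + 7 = 22 of 45, so 7.33 responders and 7.67 non-responders are expected per group. The squared deviations sum to 11.11 + 13.44 + 0.11 = 24.67. Chi-square = 24.67 × (1/7.33 + 1/7.67) = 6.58 on 2 degrees of freedom, p = 0.037 (exact p = 0.046). The stated value below 0.05 is thus reproduced, as a p-value for those exact counts. Group 1 against 2 gives Fisher p = 0.027 and Pearson p = 0.011. Group 1 against 3 (Fisher p = 0.45) and 2 against 3 (Fisher p = 0.26) do not reach 0.05.

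**Effect of the window, Group 2 minus Group 1.**

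- Weeks 1-4: R − L = 73.3 − 26.7 = 46.7 points.
- Weeks 5-8: [cR + (1−c)L] − [cL + (1−c)R] = (2c − 1)(R − L).
- Weeks 1-8, the mean of the two periods: c(R − L).

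| Carry-over c | Weeks 5-8 (points) | Weeks 1-8 (points) | Weeks 1-8: Group 1 v 2 | Fisher power, weeks 1-8 |
|---|---|---|---|---|
| 0 | −46.7 | 0 | 50.0% v 50.0% | 1.7% |
| 0.25 | −23.3 | 11.7 | 44.2% v 55.8% | 4% |
| 0.5 | 0 | 23.3 | 38.3% v 61.7% | 13% |
| 0.75 | 23.3 | 35.0 | 32.5% v 67.5% | 32% |
| 1 | 46.7 | 46.7 | 26.7% v 73.3% | 60% |

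On weeks 1-4 the same comparison has 60% power by Fisher and 74% by Pearson, whatever c is. A second model, with each patient's log rate ratio normal on each side (SD 0.4-0.8, left/right correlation 0-0.8), gives weeks 1-8 Fisher power of 1.6%, 5-6%, 16-23%, 36-44% and 60% down the rows. For a three-group chi-square with Group 3 held at 7/15, power is 66% on weeks 1-4 and, on weeks 1-8 with no carry-over, 5-9%.

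**Within-patient analysis.** Take each patient's first-period minus second-period log rate. Its expectation is (1−c)(L − R) in Group 1 and (1−c)(R − L) in Group 2. Half the difference between the group means is (1−c)(R − L), and any common period effect cancels. This is strongest where the weeks 1-8 contrast is weakest, and the reverse.

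**Illustrative power on rescue counts.** Assumed: Poisson counts, 14 baseline days, 28 days per period, log-SD 0.4-0.8, correlation 0-0.8, two-sided 0.05. Baseline use is taken as 0.3-4 doses a day. The low end reflects Section 3, where exacerbations may come only several times a week, if each takes one dose.

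| Analysis | No carry-over | Half | Full |
|---|---|---|---|
| Between groups, weeks 1-4 v baseline | 31-91% | 31-91% | 31-91% |
| Between groups, weeks 1-8 v baseline | about 5% | 15-54% | 40-90% |
| Within patient, left v right | 78-100% | 38-100% | about 5% |

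At 75% carry-over the within-patient range is 14-100%.

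**The case against.** This is a pilot meant to gauge a signal, and side is not among the primary, secondary or exploratory objectives. That stands, and it limits the weight of the point.

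The harm is also conditional twice: it needs the assumed counts to be four-week side rates, and it needs a weeks 1-8 window. The plan states neither. The counts are attached to groups that start on a side, so whole-course rates are a natural reading, and then nothing is diluted. That stands too. But the contrast would then show whether starting right beats starting left after equal time on each side, which is not the question used to justify the groups.

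Carry-over is unknown. Treatment is taken on demand and judged after fifteen minutes, so limited carry-over is plausible, but the documents do not settle it. Nor is weeks 1-4 free of cost. When carry-over is near complete, weeks 1-8 averages more days and has somewhat more power: with baseline use of 1-4 doses a day, 71-90% against 64-90% at full carry-over. If the two periods carry independent noise, with correlation ρ between them, the break-even carry-over is √((1+ρ)/2): 0.95 at ρ = 0.8 and 0.77 at ρ = 0.2. It is therefore safer to say that the contrast survives near full carry-over than only at full carry-over.

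A reader might infer that the design cannot answer the left/right question, or that its power is about 5%. The documents do not support that. The diary is daily and collected at week 4, so the clean comparison remains available. The low figures belong to one permitted window under one reading of the counts.

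**Conclusion.** The point holds as a gap between design and analysis that should be fixed. Sections 4 and 7 together describe an opposite-order crossover in Groups 1 and 2, while the plan frames only a between-group count with no window. If 4/15 and 11/15 are four-week side rates, the weeks 1-8 contrast is roughly carry-over times 46.7 points, and weeks 5-8 reverses the sign when there is no carry-over. If they are whole-course rates, the size is kept but the meaning changes to starting order.

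The power figures are illustrations: the documents give no side-specific rate, SD, correlation, carry-over or test. The algebra does not depend on the SD, correlation or test. Confidence is medium, because the size turns on an unstated reading and unknown carry-over. It should not be inferred that the main result is compromised: the principal comparison of rescue use with baseline does not depend on the left/right contrast.

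**What to change.** 1. State that the between-group side comparison uses weeks 1-4 against baseline, before the switch.
2. Add a within-patient left-versus-right analysis of the daily rescue counts in Groups 1 and 2, with side, period and patient effects, and state that it assumes limited carry-over.
3. Allocate patients to the groups from a random list, so that the weeks 1-4 contrast does not reflect who was placed where.

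Items 1 and 2 are wording and use diary data already collected at weeks 4 and 8. Item 3 changes how patients are assigned and needs a small amendment. No visits are added.

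Downsides: weeks 1-4 gives up some power against weeks 1-8 if carry-over is near complete, and the within-patient analysis has no power if it is complete. The two analyses cover each other's weak ground, which is the reason to plan both.

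As clarifications only, Section 4 should give Group 3's schedule and Section 7 should name the test behind the 0.05 statement.

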State Trait Anxiety Inventory	X		X	X	X
COMPASS 31-score			X	X	X
Noninvasive Vagal Neural Stimulation (VNS) device dispensed		X			
Follow-up medical history, including review of adverse events			X		X
12-lead EKG	X		X		
Urine pregnancy test	X		X		

Specific Tests and Questionnaires

- Pregnancy test: Women of childbearing potential must have a negative urine pregnancy test.
- 12-lead EKG: To rule out any abnormal baseline electrocardiogram such as second and third degree heart block, atrial fibrillation, atrial flutter, recent history of ventricular tachycardia or ventricular fibrillation, or clinically significant premature ventricular contraction, history of prolonged QT interval or a history of clinically significant arrhythmia.
- Gastroparesis Cardinal Symptom Index (GCSI) Daily Diary:²⁶ Consists of five core symptoms (nausea, vomiting, early satiety, postprandial fullness, upper abdominal pain).
 Each night, participants grade the severity of symptoms over the prior 24 hours. The GCSI-DD core symptom composite score (an average of the five core symptoms) is designed to detect clinical improvement in symptoms of gastroparesis and to be used as a PRO outcome for clinical trials.
- Rescue medication daily diary: Must contain the name of the antiemetic medications, dosage, frequency and number of pills during the day.
- Gastrointestinal Symptom Rating Scale (GSRS): ²⁷ The GSRS is a disease-specific instrument of 15 items combined into five symptom clusters depicting Reflux, Abdominal pain, Indigestion, Diarrhea, and Constipation. The GSRS has a seven-point graded Likert-type scale where 1 represents the absence of troublesome symptoms and 7 represents very troublesome symptoms. The reliability and validity of the GSRS are well-documented and normative values for a general population are available.
- Patient Assessment of Upper Gastrointestinal Disorders-Symptoms (PAGI-SYM): ²⁸ The self-reported questionnaire is composed of 20 items and 6 subscales. The severity of each symptom item over a 2-week recall period is scored from 0 (none or absent) to 5 (very severe). The GCSI, a 9-symptom survey relevant to gastroparesis stratified in 3 subscales nausea/vomiting, fullness/early satiety, and bloating, is contained in the PAGI-SYM. The GCSI correlates with patient severity ratings and is responsive to changes in overall symptoms. Two additional items for constipation and diarrhea also will be recorded and scored and their main symptom will be determined.

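### A 50% fall in rescue doses cannot by itself show better nausea control, because patients on treatment must use the device and wait before rescue and patients in the run-in need not

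*Combined protocol and SAP*

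**What the plan says.** Section 7 (Study Statistics) gives two primary measures, and both count doses. Under outcome measures: "The primary outcome measure is the average daily use of rescue medications for exacerbation of nausea/vomiting". Under sample size justification: "Improvement in nausea control, as defined by a 50% reduction n the number of weekly doses of rescue medications, compared with baseline". Neither contains a nausea score.

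Section 4 (frequency and duration of nVNS treatment) changes how rescue is reached during the 8 treatment weeks: "The patient will be instructed to use the nVNS in place of the rescue medications". When nausea is bad enough to want rescue, "they will first use the device on one side of the neck for two 2minute stimulations and wait fifteen minutes". If that does not help, "they will stimulate with an additional 2 stimulations and wait for another fifteen minutes". Then: "If there is no improvement rescue medication will be used". In the screening run-in, patients record as-needed rescue in a daily diary, with no device and no waiting rule.

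Nausea itself is measured. The GCSI-DD includes a nausea item: "Each night, participants grade the severity of symptoms over the prior 24 hours". It is kept in the run-in, during treatment and for two weeks afterwards, but Section 2 (Objectives) and Section 7 do not name it. PAGI-SYM, which has a nausea/vomiting subscale, is listed as exploratory.

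The study is open label. All three groups in Section 7 are stimulated, and no sham or wait-only period is described.

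**The concern.** The endpoint counts the behaviour that the treatment instruction changes. An attack that would have been medicated at once in the run-in must, on treatment, pass through one or two rounds of stimulation and waiting first. If it eases in that time for any reason (natural course, placebo response or the device), no dose is counted. The before-after difference therefore mixes a device effect with the effect of the instruction.

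This matters because of the label. The hypothesis stated just before Section 2 is relief of nausea, and Section 7 presents the dose reduction as nausea control. A report could follow that wording and claim symptom benefit from a count that does not measure symptoms.

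**Working it through.** **1. The plan's own figure.** Section 7 assumes 4/15, 11/15 and 7/15 improving (22/45 = 49% overall) and says the type I error will be below 0.05. A 3×2 test on those counts gives Pearson chi-square 6.58 on 2 df, p = 0.037; the exact test gives p = 0.046. The figure reproduces as a p-value for one assumed between-group result. It says nothing about the before-after reading.

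**2. Delay before rescue (Section 4).** One round is 2 × 2 + 15 = 19 minutes. Two rounds are 19 + 19 = 38 minutes, taking the second pair of stimulations as 2 minutes each, a length the text does not repeat. In the run-in the delay is 0.

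**3. Share of attacks that could end within the wait with an inert device.** The documents give no attack duration. Assume that attacks resolve at a constant rate with median T minutes, and that in the run-in rescue is taken at the moment when, on treatment, the device would be started. Share ending within 38 minutes = 1 − 2^(−38/T):

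| T (min) | Share |
|---|---|
| 30 | 58% |
| 38 | 50% |
| 60 | 36% |
| 120 | 20% |
| 240 | 10% |

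This applies the wait to every attack, which may not hold: "nVNS can be used up to, but no more than, 8 times a day". The unit is not defined. Counted as single stimulations, the cap covers 8/4 = 2 full sequences a day; counted as two-stimulation rounds, 8/2 = 4 rounds, again 2 full sequences; counted as full sequences, 8. Section 5 admits patients who use rescue up to four times a day. If attacks beyond the cap carried no wait, a patient with four attacks a day and two covered would have half the share: 58% × 2/4 = 29%, or 10% × 2/4 = 5%.

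**4. From a share to a responder rate.** A mean fall is not a responder rate, so an inert device was simulated. Inputs, all assumed except the period lengths: m doses a week; a 2-week run-in with Poisson mean 2m; 8 treatment weeks with Poisson mean 8m(1 − s), where s is the share of attacks left unmedicated because of the wait and the instruction. A responder has a weekly rate on treatment of at most half the patient's own run-in rate.

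| s | m = 7 | range, m = 3 to 14 |
|---|---|---|
| 20% | 5% | 1–16% |
| 30% | 14% | 6–25% |
| 40% | 29% | 21–37% |
| 50% | 52% | 51–52% |

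At m = 7, the plan's lowest assumed rate (4/15 = 27%) is reached at about s = 40%, and its overall 49% at about s = 50%. At s = 20%, few such responders are expected.

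**5. Between-group comparison.** The delay is common to all three groups. With equal inert responder rates of 10%, 30% and 50% in every group, the simulated rejection rate of the three-group test at the 5% level is 3.4%, 5.2% and 5.0%. The type I error is not materially inflated.

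**The case against.** The strongest reply is that the endpoint matches the principal objective. Section 2 asks whether acute nVNS reduces rescue use, and Section 3 (Background) offers the device as an alternative to rescue, so substitution is the strategy under test. This stands: counting doses is legitimate, and the defect lies in the label and in what is inferred from it.

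Nor is nausea ignored. Rescue stays available when there is no improvement, so a patient who endures unrelieved nausea is departing from the instruction. PAGI-SYM at screening and weeks 4, 8 and 10, and a global impression questionnaire on treatment, could reveal worsening. This also stands, but no threshold defines improvement within an attack, spontaneous easing qualifies, and none of these measures governs the primary claim.

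Three stronger readings are tempting and unsupported:

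- A reader might infer that an inert device would by itself produce a 50% fall. Under the model above that needs a median attack of 38 minutes or less with the wait applied to every attack, and the documents give no duration.
- A reader might infer that the group comparison is biased. Step 5 shows that a delay shared by all groups does not do this.
- A reader might infer that the responder definition must also require GCSI-DD nausea no higher than in the run-in. That is a debatable trade-off. With nausea truly unchanged, about half of patients would pass by symmetry, so if the criteria were independent a 52% inert rate would fall only to 52% × 0.5 = 26%. Fading attacks would still count, and about half of true rescue responders with unchanged background nausea would fail by chance.

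**Conclusion.** The concern holds as a matter of labelling and interpretation. A 50% fall in rescue doses shows reduced rescue use under a changed rule; it cannot, alone, show nausea control. Some fall could occur with an inert device, and nothing in the design separates that part from a device effect. This affects each group's responder rate and the before-after reading on which the principal objective rests.

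The direction follows from the documents. The size does not: 10% to 58% of attacks ending within 38 minutes is a range over assumed medians of 240 to 30 minutes, with constant-rate resolution and the full wait every time. The simulated responder rates add an assumed dose rate and an assumed unmedicated share. Nothing here shows that the trial would give a false positive result, or that rescue use is the wrong thing to count.

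**What to change.** 1. In Section 7, name the endpoint as a 50% reduction in weekly rescue doses from baseline and drop the nausea-control label.
2. Name change in mean daily GCSI-DD nausea as a key secondary endpoint, reported beside the primary result. Compare the run-in with the same treatment weeks used for the dose count, and state which weeks those are, since the plan does not define the window for weekly doses. Allow a claim of nausea relief only if this score also improves.
3. Whatever the GCSI-DD shows, describe the rescue result as the effect of the device plus the instruction to use it before rescue. Acknowledge in the plan and the report that the rescue rules differ between the two periods.

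No composite responder is required, and no change to the clinical rule is proposed. The diaries are already planned, so no new data are needed. The cost is a little more analysis and a more limited conclusion.
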